7.2. Sensitivity Analysis of Primary Analysis

The primary analysis will be performed in FAS. Any missing values will be imputed using the last observation carried forward (LOCF) method. Analyses will be performed in the same fashion if no imputation takes place.

7.3. Secondary Analyses of Primary Endpoint

Following analyses will be performed in FAS and PPS:

- Summary statistics will be calculated for each treatment group. Missing values will not be imputed.
- For percent change in the mean IEF per 24 hours from baseline at each week, mixed-effect models for repeated measures (MMRM) will be performed using treatment groups, evaluation time points (Week 4 and Week 8 of treatment), and interactions between the treatment group and the evaluation time point as fixed effects, and allocation factors (status of urinary incontinence [SUI or MUI], mean IEF per 24 hours [≥ 2 per day or < 2 per day]) and age (≥ 60 years or < 60 years) as covariates. Thus, the least mean square (LS Mean) in each treatment group and the difference in the LS mean between each dose group and the placebo group and the two-sided 95% CI will be estimated at Week 8 of treatment. Unstructured covariance structure will be assumed, and toeplitz type will be used in case of no convergence. If convergence is still not achieved, the First-order autoregressive → Compound symmetry → Variance component will be used in this order. The Kenward-Roger method (2009)⁴⁾ will be used to calculate degrees of freedom.
- Intergroup comparison will be conducted using the placebo group as the control by the van Elteren test⁵⁾ using Wilcoxon rank sum test and allocation adjustment factors and age (< 60 years and ≥ 60 years) as strata. If any stratum includes a group with 0 patient, the test will be conducted by excluding age from the strata. The van Elteren

test will be performed in two patterns, i.e., a pattern in which allocation adjustment factors at the time of enrollment are used as strata (analysis in the FAS only) and a pattern in which allocation adjustment factors recorded in CRF are used as strata. Missing data will be imputed using LOCF.

• The time profile of percent change from the baseline will be graphically presented by treatment group.

7.4. Analyses Based on Allocation Factors

Following analyses will be performed in PPS:

- Primary endpoints will be analyzed by status of urinary incontinence (SUI, MUI).
- Primary endpoints will be analyzed by mean IEF per 24 hours (≥ 2 per day, < 2 per day).

8. ANALYSES OF SECONDARY ENDPOINT

The below shows the summary of analyses for secondary endpoints. A confidence coefficient of 95% will be used to present the confidence interval.

8.1. Efficacy Analysis

Following analyses will be performed by treatment group in FAS and PPS:

8.1.1. Mean IEF per 24 Hours

- Summary statistics will be calculated for measured values at each evaluation time point (at the time of enrollment, Weeks 4 and 8 of treatment) and percent changes (Week 4 of treatment) as well as changes (Weeks 4 and 8 of treatment) from baseline. Summary statistics of the mean frequency of SUI episode per week will also be calculated.
- For percent changes (Weeks 4 and 8 of treatment) and changes (Weeks 4 and 8 of treatment) from baseline to each time point of evaluation, student's t-test, Wilcoxon's rank sum test, and van Elteren test using allocation adjustment factors and age (< 60 years and ≥ 60 years) as strata will be conducted using the placebo group as the control. If any stratum includes a group with 0 patient, the test will be conducted by excluding age from the strata. The van Elteren test will be performed in two patterns, i.e., a pattern in which allocation adjustment factors at the time of enrollment are used as strata (analysis in the FAS only) and a pattern in which allocation adjustment factors recorded in CRF are used as strata.
- For percent change and changes from baseline at each week, MMRM will be performed using treatment groups, evaluation time points (Weeks 4 and 8 of treatment), and interactions between the treatment group and the evaluation time point as fixed effects, and allocation factors (status of urinary incontinence [SUI or MUI], mean IEF per 24 hours [≥ 2 per day or < 2 per day]) and age (≥ 60 years or < 60 years) as covariates. Thus, the least mean square (LS Mean) in each treatment

group and the difference in the LS Mean between each dose group and the placebo group and the two-sided 95% CI will be estimated at overall evaluation time points. Unstructured covariance structure will be assumed, and toeplitz type will be used in case of no convergence. If convergence is still not achieved, the First-order autoregressive \rightarrow Compound symmetry \rightarrow Variance component will be used in this order. The Kenward-Roger method $(2009)^{4}$ will be used to calculate degrees of freedom.

• The percentage of patients with at least 50% reduction from baseline at each time point (Weeks 4 and 8 of treatment) and its 95% confidence interval (CI) will be calculated, and Fisher's exact test with placebo as the control will be conducted.

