## 3.2 Randomization and Blinding

### 3.2.1 Randomization

This study is a randomized study to be conducted by central enrollment using an interactive web response system (IWRS). Data are entered in accordance with the written procedures for IWRS.

The Investigator or Sub-investigator obtains written consent after providing an explanation to the patients. Patient numbers are 6-digit (eg., 500101). The first digit represents the protocol number (5). The following 3 digits indicate a healthcare facility code. The last 2 digits represent the order of consent at each healthcare facility. These patient numbers are used throughout the entire study. The Investigator or Sub-investigator confirms that the subjects meet the inclusion criteria and do not meet the exclusion criteria for the enrollment in the observation period. Then, the patients concerned are enrolled in the observation period through IWRS. Similarly, for the enrollment in the treatment period, the patients concerned are enrolled in the treatment period through IWRS after the confirmation that they meet the inclusion criteria and do not meet the exclusion criteria for the enrollment in the treatment period. At the time of enrollment in the treatment period, subjects are randomly assigned to 3 mg of TAS-303, 6 mg of TAS-303 or placebo with a ratio of 1:1:1 through IWRS based on the stochastic minimization method.

Patients are stratified using the following allocation adjustment factors.

- Mean number of urinary incontinence per 24 hours at the time of enrollment in the treatment period (less than 2/day and 2 or more/day)
- Condition of urinary incontinence (SUI/MUI)

Through IWRS, a study drug is assigned to each patient, the study site is informed of the drug number assigned to the patient and the instructions regarding the prescription of the study drug are given. For details, see written procedures for IWRS.

If by any chance the study drug different from the drug number assigned by IWRS is dispensed to a patient, the Sponsor must be contacted immediately. The study site must record the cause of the error in prescription or dispensing of the study drug. If administration of the study drug was started in the group different from the assigned one, the administration is continued.

When the “Section 4.3 Patient Discontinuation Criteria” are met, the items related to the discontinuation are promptly entered into IWRS.

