8.1.2. Urinary Incontinence Amount in 1-Hour Pad Test

- Summary statistics will be calculated for measured values at each evaluation time point (at the time of enrollment in the treatment period and Week 8 of treatment) and percent changes (Week 8 of treatment) as well as changes (Week 8 of treatment) from baseline.
- For percent change from baseline and change from baseline to each evaluation time point (Week 8 in the treatment period), student's t-test will be conducted using the placebo group as the control.
- The percentage of patients with an observed value of ≤ 2.0 g at Week 8 of treatment, and its 95% CI will be calculated.
- The percentage of patients with at least 50% reduction from baseline at Week 8 of treatment and its 95% CI will be calculated, and Fisher's exact test with placebo as the control will be conducted.

8.1.3. Mean Number of Pads Used per 24 Hours (Only for Patients Who Had Ever Used Incontinence Pads)

- Summary statistics for the observed value (Weeks 4 and 8 of treatment), percent change (Weeks 4 and 8 of treatment) from baseline, and change (Weeks 4 and 8 of treatment) from baseline at each time point will be calculated.
- For percent change from baseline and change from baseline to each evaluation time point (Weeks 4 and 8 of treatment), student's t-test will be conducted using the placebo group as the control.

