8.1.5. Patient Global Impression of Improvement (PGI-I)

- The percentage of patients by score on the 7-point scale assessment at the time of enrollment in the treatment period, and Weeks 4 and 8 of treatment will be calculated.
- The percentage of patients with an improvement (patients selecting "Very much better," "Much better," or "A little better" or patients selecting "Very much better" or "Much better") at the time of enrollment in the treatment period and Weeks 4 and 8 of treatment and its 95% CI will be calculated, and Fisher's exact test with placebo as the control will be conducted.
- The proportion of improvement ("Very much better" and "Much better") at the time of enrollment in the treatment period and Weeks 4 and 8 of treatment and 95% CI will be calculated, and Fisher's exact test with placebo as the control will be conducted.

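### The 50% responder and PGI-I comparisons rest on an unstratified Fisher's exact test with no between-group effect estimate, and pad-test continence is not compared at all

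*SAP*

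**What the plan says.** Protocol 3.2.1 randomises "with a ratio of 1:1:1 through IWRS based on the stochastic minimization method" and adds: "Patients are stratified using the following allocation adjustment factors". The two factors are baseline leak frequency (below 2, or 2 and above, per day) and type of incontinence (SUI or MUI).

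SAP 8.1.1, 8.1.2, 8.1.7 and 8.1.8 each give the percentage of patients with at least a 50% reduction, with a 95% CI, followed by Fisher's exact test against placebo: "Fisher's exact test with placebo as the control will be conducted". SAP 8.1.5 treats PGI-I improvement the same way: "its 95% CI will be calculated, and Fisher's exact test with placebo as the control will be conducted". None of these sections names a stratum, a difference in proportions or an odds ratio.

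SAP 8.1.2 also plans "The percentage of patients with an observed value of ≤ 2.0 g at Week 8 of treatment" with its CI, and stops there. No comparison with placebo follows.

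For diary frequency, 8.1.1, 8.1.7 and 8.1.8 do use the allocation factors and age: as strata in the van Elteren test and as covariates in the MMRM, which yields differences in LS means with 95% CIs. SAP 8.1.9 repeats 8.1.1 to 8.1.8 in PPS within levels of each factor. Protocol 13.1.3.3.1 had planned only proportions and CIs for these binary endpoints.

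**The concern.** There are two separate costs.

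- **No effect size.** A Fisher p-value beside three per-group intervals does not tell the reader how large the difference from placebo is or how precisely it is known. A phase IIa trial that is meant to help estimate a recommended dose (Protocol 1.4.3) needs that figure. The Protocol synopsis names PGI-I as a main secondary endpoint, and Protocol 2.3.2.1 lists the 50% responder proportion and pad-test continence.
- **Some lost power.** Fisher's test runs below its nominal level at this sample size. It also ignores factors that the SAP uses when the same diary outcome is analysed as a continuous variable in the same sections.

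**Working it through.** **1. The plan's own figure.** SAP 2.2.2 gives a difference of 20, SD 35, two-sided 2.5% per test, 90% power and about 5% withdrawal. The normal formula n = 2 × (z0.9875 + z0.90)² × (35/20)² = 2 × (2.241 + 1.282)² × 3.0625 gives 77 per group after rounding up. The noncentral t gives 78 (power 90.3%). Then 78/0.95 = 82.1, so 83 per group and 3 × 83 = 249, stated as about 250. The sample size reproduces and is not in dispute. I use 78 evaluable per group below.

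**2. Illustrative responder rates.** The plan states none. Assume normal percent changes with SD 35, the quoted placebo mean of -41.86 and an active mean of -41.86 - 20 = -61.86. P(change ≤ -50) is then:

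- Placebo: Φ((-50 + 41.86)/35) = Φ(-0.233) = 40.8%
- Active: Φ((-50 + 61.86)/35) = Φ(0.339) = 63.3%

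The odds ratio is (0.633/0.367)/(0.408/0.592) = 2.5.

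**3. Exact size and power.** I enumerated all outcomes of two binomials with n = 78 each. The nominal level is two-sided 5%, an assumption, since the SAP states no level for these tests.

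| Test | True size at 40.8% | Power, 40.8% vs 63.3% |
|---|---|---|
| Fisher's exact | 3.5% | 74.9% |
| Mantel-Haenszel chi-square, unstratified | 4.7% | 79.7% |

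The gap is 79.7 - 74.9 = 4.8 points. No strata are involved, so this part is due to discreteness alone. At 79 per group, for common rates from 10% to 60%, Fisher's size lies between 2.8% and 3.4%.

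**4. What stratifying adds.** I simulated four strata of 20, 19, 20 and 19 per group, odds ratio 2.5, 200,000 runs per row. The stratum rates and sizes are assumptions.

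| Assumed placebo rates by stratum | Fisher | Unstratified chi-square | Stratified CMH | Fisher to chi-square | Chi-square to CMH |
|---|---|---|---|---|---|
| 0.408 in all four | 75.1% | 79.8% | 79.9% | 4.7 | 0.1 |
| 0.55 / 0.45 / 0.35 / 0.29 | 71.6% | 76.8% | 78.9% | 5.2 | 2.1 |
| 0.65 / 0.50 / 0.30 / 0.19 | 62.7% | 68.9% | 75.4% | 6.2 | 6.5 |

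Under the null, CMH stayed between 4.9% and 5.2% in all three rows, while Fisher fell from 3.5% to 3.1% and 2.3%. A more extreme assumption (79 per group, strata of 24/16/24/15, log-odds effect of 1.5 for each factor) gave 56.5% for Fisher, 63.5% for the unstratified chi-square and 72.2% for CMH, so stratifying added 8.7 points there. These runs fix equal stratum sizes across arms. Minimisation balances the factors only approximately.

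**The case against.** The strongest case on the other side is that this is a preference about exploratory secondary endpoints.

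- **Low stakes.** Fisher's test protects the type I error. SAP 11.5 controls multiplicity for the primary objective only, so no decision rule hangs on these p-values. This stands, and it limits the weight of the point. It does not supply the missing effect estimate.
- **Unadjusted comparison is common in this SAP.** A reader might infer that the binary endpoints are the lone exception to a stratified plan. They are not: the primary t-test (7.1) and the tests for pad-test amount, pad count, ICIQ-SF and I-QOL (8.1.2 to 8.1.4, 8.1.6) are also unstratified. The contrast holds only against the diary-frequency endpoints.
- **Cause of the conservatism.** A reader might infer that the test is conservative because it ignores the strata. The first row of the simulation shows otherwise: with non-prognostic factors, stratifying gains almost nothing and Fisher still loses about 5 points.
- **Assumed inputs.** The stratum rates are not in the documents. The normal model is also crude: it puts Φ((-100 + 61.86)/35) = 13.8% of active patients below -100%, which cannot occur. The figures are therefore illustrative.
- **Subgroup results exist.** SAP 8.1.9 reports within levels of each factor, but in PPS only and without a pooled adjusted effect.
- **Timing.** SAP version 2.0 was issued before key code breaking. Version 3.0, dated September 4, 2018, adds further analyses. Replacing a prespecified test with a more powerful one at that stage would cost credibility. This stands, and it is why the fix adds rather than replaces.

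**Conclusion.** The point holds as a modest one. The responder and PGI-I comparisons provide no between-group estimate with an interval, and pad-test continence has no comparison. Neither observation needs any assumption.

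On power, the loss is about 5 points from Fisher's discreteness, given rates near 41% and 63%, 78 per group and nominal 5%. Stratifying recovers roughly a further 0 to 6 points across the scenarios at 78 per group, and nearly 9 under the most extreme one tried. Where this trial lies in that range depends on how prognostic the two factors are, which the documents do not state.

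A reader might infer that the plan's error rate or its main conclusion is at risk. The documents do not support that: Fisher's test errs on the safe side, and the primary t-test and sample size are untouched. It would also be wrong to say that every binary endpoint is tested by Fisher, since pad-test continence is not tested. SAP section 12 refers to a separate Table and Figure Plan that lists all analyses. It is not among the documents, so it may hold more detail.

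**What to change.** In SAP 8.1.1, 8.1.2, 8.1.5, 8.1.7 and 8.1.8:

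- Add a Cochran-Mantel-Haenszel test of each dose against placebo, stratified by the two allocation factors. Use CRF values in PPS, and both CRF and IWRS values in FAS, as SAP 6.2.3 requires.
- Report the Mantel-Haenszel risk difference against placebo with a 95% CI.
- Allow age (below 60, 60 and above) as a further stratum where cells permit, in line with the van Elteren test.
- Keep Fisher's test as the prespecified analysis and for sparse tables.
- Apply the same comparison to pad-test continence at Week 8.
- If the key code has been broken, record the addition in the change log as newly planned, as SAP section 10 requires.

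The data are already collected and the programming is a few lines. The downside is a few more secondary outputs, and an analysis added late that must be labelled as such.

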8.1.2. Urinary Incontinence Amount in 1-Hour Pad Test

- Summary statistics will be calculated for measured values at each evaluation time point (at the time of enrollment in the treatment period and Week 8 of treatment) and percent changes (Week 8 of treatment) as well as changes (Week 8 of treatment) from baseline.
- For percent change from baseline and change from baseline to each evaluation time point (Week 8 in the treatment period), student's t-test will be conducted using the placebo group as the control.
- The percentage of patients with an observed value of ≤ 2.0 g at Week 8 of treatment, and its 95% CI will be calculated.
- The percentage of patients with at least 50% reduction from baseline at Week 8 of treatment and its 95% CI will be calculated, and Fisher's exact test with placebo as the control will be conducted.

8.1.3. Mean Number of Pads Used per 24 Hours (Only for Patients Who Had Ever Used Incontinence Pads)

- Summary statistics for the observed value (Weeks 4 and 8 of treatment), percent change (Weeks 4 and 8 of treatment) from baseline, and change (Weeks 4 and 8 of treatment) from baseline at each time point will be calculated.
- For percent change from baseline and change from baseline to each evaluation time point (Weeks 4 and 8 of treatment), student's t-test will be conducted using the placebo group as the control.

8.1.4. ICIQ-SF score

- Summary statistics for the total score (at the time of enrollment in the observation period, at the time of enrollment in the treatment period, and Weeks 4 and 8 of treatment) and change (Weeks 4 and 8 of treatment) from baseline at each time point will be calculated.
- Summary statistics for the subscale score (at the time of enrollment in the observation period, at the time of enrollment in the treatment period, and Weeks 4 and 8 of

treatment) and change (Weeks 4 and 8 of treatment) from baseline at each time point will be calculated.

- For the change in the total score from baseline to each evaluation time point (Weeks 4 and 8 of treatment), student's t-test will be conducted using the placebo group as the control.
- For the change in the subscale score from baseline to each evaluation time point (Weeks 4 and 8 of treatment), student's t-test will be conducted using the placebo group as the control.

8.1.5. Patient Global Impression of Improvement (PGI-I)

- The percentage of patients by score on the 7-point scale assessment at the time of enrollment in the treatment period, and Weeks 4 and 8 of treatment will be calculated.
- The percentage of patients with an improvement (patients selecting "Very much better," "Much better," or "A little better" or patients selecting "Very much better" or "Much better") at the time of enrollment in the treatment period and Weeks 4 and 8 of treatment and its 95% CI will be calculated, and Fisher's exact test with placebo as the control will be conducted.
- The proportion of improvement ("Very much better" and "Much better") at the time of enrollment in the treatment period and Weeks 4 and 8 of treatment and 95% CI will be calculated, and Fisher's exact test with placebo as the control will be conducted.

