## Synopsis

Name of Sponsor:	Taiho Pharmaceutical Co., Ltd.
Name of Investigational Product:	TAS-303 [REDACTED]
Non-proprietary name:	-
Title of Study:	
An early phase II study of TAS-303 in female patients with stress urinary incontinence	
Protocol Number:	10060050
Phase of Development:	Phase IIa
Indication:	Stress urinary incontinence (SUI)
Background/Rationale:	
SUI is a complaint of involuntary leakage of urine at the time of exertion or exercise, or during sneezing or coughing.
 
According to Clinical Guideline for Female Lower Urinary Tract Symptoms, although anatomical factors of SUI cannot be improved by medication, resting urethral pressure has been reported to be lower in SUI patients than in women at the same age without urinary incontinence and therefore, theoretically, SUI can be treated by improving the low urethral closure pressure.
 
[REDACTED]
 
[REDACTED]
 
[REDACTED]

Study Objective/Endpoints:	
Primary: To examine the efficacy of TAS-303 using the rate of change in the number of urinary incontinence as an index and placebo as control in female patients with SUI
 
Secondary:
 
 
(1) To examine the efficacy of TAS-303 using changes in the variables including the International Consultation on Incontinence Questionnaire-Short Form (ICIQ-SF) score or the Incontinence Quality of Life (I-QOL) score as indices and placebo as control in female patients with SUI
 
(2) To examine the dose response of TAS-303 in improvement of urinary incontinence in female patients with SUI in an exploratory manner
 
(3) To examine the safety of TAS-303 using the status of onset of adverse events and other indices in female patients with SUI
 
 
Primary Endpoint:
 
 
• Rate of change in mean number of urinary incontinence per 24 hours (Week 8 in treatment period)
 
 
Main Secondary Endpoints:
 
 
• Mean number of urinary incontinence per 24 hours
 

	
 
Amount of urinary incontinence by 1-hour pad test
 
Mean number of used pads per 24 hours
 
ICIQ-SF score
 
Patient Global Impression-Improvement: PGI-I
 
I-QOL score
 
Status of onset of adverse events and adverse reactions
 

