#### 11.1.2 PGI-I

The patients' impression of improvement of urinary incontinence is evaluated using PGI-I. The content of PGI-I is shown in [APPENDIX 2 Patient Global Impression-Improvement: PGI-I](#).

The improvement of PGI-I is defined as the selection of "very much better", "much better" or "a little better".

The Investigator or Sub-investigator instructs patients to evaluate the improvement of urinary incontinence at the evaluation time point using the following 7-point scale. The Investigator or Sub-investigator should be careful not to bias the evaluation by, for example, being close to patients or talking to them while they are evaluating.

- Very much better
- Much better
- A little better
- No change
- A little worse
- Much worse
- Very much worse

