### 13.1.3.3 Secondary Endpoint Analysis

#### 13.1.3.3.1 Efficacy Analysis

The following analyses are performed for each treatment group in FAS and PPS.

(1) Mean number of urinary incontinence per 24 hours

- Summary statistics of measured values, rate of change from baseline and amount of change at each evaluation time point are calculated.
- The rate of change from baseline is analyzed using MMRM and the therapeutic effect of TAS-303 at all evaluation time points is estimated.
- The proportion of subjects with 50% or greater improvement in the rate of change from baseline and 95% CI at each evaluation time point are calculated.

(2) Amount of urinary incontinence by 1-hour pad test

- Summary statistics of measured values, rate of change from baseline and amount of change at each evaluation time point are calculated.
- The proportion of subjects with 2.0 g or less measured values at Week 8 of the treatment period and 95% CI are calculated.
- The proportion of subjects with 50% or greater improvement in the rate of change from baseline at Week 8 of the treatment period and 95% CI are

calculated.

- (3) Mean number of used pads per 24 hours (only in patients who used incontinence pads)
  - Summary statistics of measured values, rate of change from baseline and amount of change at each evaluation time point are calculated.
- (4) ICIQ-SF score
  - Summary statistics of total score and amount of change from baseline at each evaluation time point are calculated.
  - Summary statistics of the score for each item and amount of change from baseline at each evaluation time point are calculated.
- (5) Patient Global Impression-Improvement (PGI-I)
  - Proportion for each rating on 7-point scale at each evaluation time point is calculated.
  - Proportion of improvement (“very much better”, “much better”, “a little better”) at each evaluation time point and 95% CI are calculated.
- (6) I-QOL score
  - Summary statistics of total score and amount of change from baseline at each evaluation time point are calculated.
  - Summary statistics of the score of each area and amount of change from baseline at each evaluation time point are calculated.
- (7) Analysis by allocation factor
  - The secondary endpoints are analyzed for each condition of urinary incontinence (SUI and MUI).
  - The secondary endpoints are analyzed for each category of mean number of urinary incontinence per 24 hours (less than 2/day and 2 or more/day).
- (8) Mean number of SUI per 24 hours

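### SAP 8.1.5 tests PGI-I, a seven-level ordered main secondary endpoint, only on yes/no cuts; an ordinal comparison should be added beside the responder tests

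*SAP*

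**What the plan says.** Protocol 11.1.2 asks patients to "evaluate the improvement of urinary incontinence at the evaluation time point using the following 7-point scale", running from 'very much better' to 'very much worse'. The Synopsis lists PGI-I under "Main Secondary Endpoints". The same Protocol section fixes the responder definition: "The improvement of PGI-I is defined as the selection of 'very much better', 'much better' or 'a little better". SAP 6.1.1.1.2 repeats that top-3 definition.

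Protocol 13.1.3.3.1(5) plans "Proportion for each rating on 7-point scale at each evaluation time point" and the proportion improved with a 95% CI, and names no test.

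SAP 8.1.5 tabulates "The percentage of patients by score on the 7-point scale assessment at the time of enrollment in the treatment period" and at Weeks 4 and 8, again with no test. For the proportion improved, "its 95% CI will be calculated, and Fisher's exact test with placebo as the control will be conducted". That bullet covers both the top-3 cut and a top-2 cut. A further bullet then repeats the top-2 cut: "The proportion of improvement ('Very much better' and 'Much better') at the time of enrollment in the treatment period". The SAP change table shows that the top-2 analysis entered with version 3.0 as an additional analysis.

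**The concern.** At the top-3 cut, 'very much better' counts the same as 'a little better'. At either cut, 'very much worse' counts the same as 'no change'. The trial collects these distinctions, but no planned PGI-I test in the SAP text uses more than one boundary of the scale at a time.

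This is out of line with the rest of the SAP. The other main secondary efficacy endpoints are tested as follows:

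- Episode frequency (8.1.1): t-test, Wilcoxon, van Elteren and MMRM, with a Fisher test at 50% reduction beside them.
- Pad test (8.1.2): t-test, with a Fisher test at 50% reduction beside it.
- Pads used (8.1.3): t-test.
- ICIQ-SF (8.1.4): t-tests on the total and the component scores.
- I-QOL (8.1.6): t-tests on the total and the domains.

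Wherever else in this group a dichotomy is tested, a full-scale test accompanies it. PGI-I is the exception. What is at stake is sensitivity to an effect spread over the scale, which either cut captures only in part.

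**Working it through.** **The plan's own figure.** SAP 2.2.2 sizes the primary endpoint only: difference 20, SD 35, two-sided 2.5% per test, power 90%, withdrawal about 5%. The normal formula is n = 2(SD/difference)²(z₀.₉₈₇₅ + z₀.₉₀)² = 2 × (35/20)² × (2.241 + 1.282)², which rounds up to 77 per group. Then 77/0.95 gives 82 per group, or 246 in all. The t-based version gives 78, then 83 per group and 249. The stated 83 and about 250 reproduce. Neither document gives a power figure for PGI-I.

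**Inputs for PGI-I.** From the documents: seven levels, 1:1:1 allocation, and 83 × 0.95 ≈ 79 evaluable per arm. Assumed, because the documents are silent:

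- Two-sided 5% per test.
- Placebo percentages from best to worst level: A = 5/15/30/40/7/2/1, B = 10/20/35/30/3/1.5/0.5.
- One odds ratio (OR) shifting every cut.

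**Shift.** If c is the placebo proportion at or above a cut, the active proportion is OR·c/(1 − c + OR·c). At OR 2.0:

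- A, top 3: 2 × 0.50/1.50 = 0.667. A, top 2: 2 × 0.20/1.20 = 0.333.
- B, top 3: 2 × 0.65/1.65 = 0.788. B, top 2: 2 × 0.30/1.30 = 0.462.

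**Power** (Fisher by exact enumeration; tie-corrected Wilcoxon rank sum by simulation):

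| OR | Placebo | Fisher top 3 | Fisher top 2 | Rank, 7 levels | Gain over top 3 / top 2 |
|---|---|---|---|---|---|
| 1.8 | A | 37% | 29% | 53% | 16 / 24 |
| 1.8 | B | 32% | 37% | 52% | 20 / 15 |
| 2.0 | A | 50% | 41% | 66% | 16 / 25 |
| 2.0 | B | 42% | 49% | 67% | 25 / 18 |
| 2.2 | A | 61% | 52% | 78% | 17 / 26 |
| 2.2 | B | 51% | 61% | 78% | 27 / 17 |

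The gain is 15 to 27 points.

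**How much is the collapse itself.** Fisher's actual size in these scenarios is 3.1 to 3.5%; the rank test runs at about 5%. An uncorrected chi-square on the same cuts has size 4.6 to 5.2%. Its power at OR 2.0 is 56% (top 3) and 48% (top 2) in A, and 49% and 56% in B. Before rounding, that is 6 to 8 points above Fisher. What remains for the collapse at OR 2.0 is 66 − 56 = 10 and 66 − 48 = 18 in A, and 67 − 49 = 18 and 67 − 56 = 11 in B.

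**Sensitivity to the assumptions.**

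- Five placebo distributions, OR 1.5 to 3.0, 79 or 83 per arm: the gain over Fisher runs from about 5 to 37 points.
- Ten points moved from 'no change' to 'a little better' and ten from 'a little better' to 'much better': Fisher top 3 / Fisher top 2 / rank = 19/25/26% (A) and 22/22/28% (B). The rank test gains at most 7 points.
- Effect at one cut only, placebo 5/15/35/38/5/1.5/0.5: 20 points moved from 'no change' to 'a little better' gives rank 40% against Fisher top 3 71%. Fifteen points moved from 'a little better' to 'much better' gives rank 14% against Fisher top 2 49%. In A the first of these moves gives 36% against 68%.
- Van Elteren with eight assumed strata (2 × 2 × 2) and no prognostic effect: 64% in both A and B at OR 2.0. Prognostic strata could raise this; that was not computed.

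**The case against.** The strongest reply is that the SAP tests what the protocol defined. Protocol 2.3.2.1(5) states PGI-I as proportions, 13.1.3.3.1(5) plans no test at all, and a responder rate is easy to interpret where a rank test alone yields a p-value. This stands as a reason to keep the top-3 comparison. It is no reason to omit a full-scale one.

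A reader might also infer several stronger points that the documents do not support:

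- *The plan loses a fixed amount of power.* No PGI-I distribution, effect size, significance level or power is given, and the sign reverses when the effect sits at one cut.
- *The whole gap comes from collapsing the scale.* Part of it is Fisher's conservatism.
- *The two cuts have no order between them.* Top 3 is the defined endpoint in Protocol 11.1.2 and SAP 6.1.1.1.2, and top 2 is a version 3.0 addition. The layout of 8.1.5 blurs this but does not remove it.
- *No ordinal test exists anywhere.* SAP section 12 says that the SAP lists major items only and leaves the rest to a separate Table and Figure Plan, which is not among the documents.
- *The ordering is ignored altogether.* The seven levels are still tabulated by arm.

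Finally, the trial was not sized on PGI-I, and SAP 11.5 confines multiplicity control to the primary objective. That limits the weight of the point.

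**Conclusion.** The point holds in a limited form. In the SAP text, PGI-I is the one main secondary efficacy endpoint without a between-group test on its full scale. Under an assumed common shift (OR 1.8 to 2.2, 79 per arm, two-sided 5%, placebo distributions A and B), a rank test has about 15 to 27 points more power than either Fisher test, including about 6 to 8 points from Fisher's conservatism. If the effect is confined to one cut, the Fisher test at that cut is better, but which cut that would be is not known in advance. This supports an ordinal test beside the responder analysis. It does not support replacing or demoting the protocol-defined comparison.

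**What to change.** In SAP 8.1.5, add for Weeks 4 and 8 a comparison of each dose with placebo on the seven ordered levels, by Wilcoxon rank sum and by van Elteren with the 8.1.1 strata and the same empty-stratum rule. Keep the top-3 proportion with its CI and Fisher test. State the top-2 cut once and label it as additional. If the ordinal test is added after key-code breaking, record it as an additional analysis under SAP section 10.

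The cost is about one sentence. The data are already collected and both tests are already specified elsewhere in the SAP. The downside is one more comparison on a secondary endpoint outside multiplicity control. A rank test also gives a p-value without a responder-type effect size, which the retained proportions supply.
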